8.3.4. Pregnancy

- Details of all pregnancies and exposure during breastfeeding, from the time of treatment through 120 days following cessation of study treatment, or 30 days following cessation of study treatment if the participant initiates new anticancer therapy.
- If a pregnancy is reported, the investigator should inform the sponsor within 24 hours of learning of the pregnancy and should follow the procedures outlined in Section 10.3, Appendix 3.
- Abnormal pregnancy outcomes (e.g. spontaneous abortion, fetal death, stillbirth, congenital anomalies, and ectopic pregnancy) are considered SAEs.
- Additional requirements for pregnancy testing during and after study intervention are located in Section 10.3, Appendix 3.
- The investigator is responsible for review of medical history, menstrual history, and recent sexual activity to decrease the risk for inclusion of a female with an early undetected pregnancy.

8.3.5. Cardiovascular and Death Events

Not applicable.

8.3.6. Complaint Handling

Lilly collects product complaints on investigational products and drug delivery systems used in clinical studies in order to ensure the safety of study participants, monitor quality, and facilitate process and product improvements.

Participants will be instructed to contact the investigator as soon as possible if he or she has a complaint or problem with the investigational product so that the situation can be assessed.

8.4. Treatment of Overdose

Refer to the IB and/or Product Label for abemaciclib for available information on the signs, symptoms, and treatment of overdose.

For dinutuximab, GM-CSF, irinotecan, and temozolomide, refer to the respective Product Label for available information on the signs, symptoms, and treatment of overdose.

8.5. Pharmacokinetics

At the visits and times specified in the SoA (Section 1.3), PK samples will be collected to determine the concentrations of:

- abemaciclib and its metabolites M2 and M20
- irinotecan and its metabolite SN-38
- temozolomide

The PK of dinutuximab and GM-CSF will not be assessed.

To ensure comprehensive PK sampling in a pediatric population, Parts A and B are designed to evaluate at least CCI [REDACTED] including at least CCI [REDACTED] and at least 2 CCI [REDACTED] If no patients CCI [REDACTED] and evaluable in the above groups, then CCI [REDACTED] will be evaluated. The number of patients 18 years of age will be capped at [REDACTED] until patient numbers in the above age groups are enrolled.

Additionally, in Part C, at least CCI [REDACTED] should be in the age group CCI [REDACTED] of age, with at least CCI [REDACTED] and at least CCI [REDACTED] [REDACTED]

Abemaciclib dosing dates and times are required to be collected 3 days prior to the PK samples. The date and exact time of collection of each PK sample must be recorded on the laboratory requisition. Beyond the first dose, PK samples may be aligned to coincide with standard laboratories when applicable, with the collection dates/times specified in the SoA (Section 1.3.3) to be used as a guide.

For patients receiving chemotherapy infusions, the PK samples should be drawn from a separate line at a peripheral access site.

A maximum of 5 samples may be collected at additional time points during the study if warranted and agreed upon between both the investigator and sponsor. Instructions for the collection and handling of blood samples will be provided by the sponsor. The actual date and time (24-hour clock time) of each sampling will be recorded.

The PK sampling schedule is designed to comply with blood volume limitations in pediatric patients. If the collection of PK samples will exceed maximum blood draw volumes for any patient, blood samples for safety will be prioritized over PK after discussion between the sponsor and the investigator.

Bioanalytical samples collected to measure investigational product concentration will be retained for a maximum of 1 year following last participant visit for the study. During this time, samples remaining after the bioanalyses may be used for exploratory analyses (such as quantification of circulating metabolites and/or protein binding work).

8.5.1. Patient Diary

A diary will be provided to patients/caregivers in order to help track date and time of each dose during cycles in which PK samples are collected. Patient diary evaluations will occur through Cycle 3 Day 1. The diary is not intended for compliance monitoring. Refer to Section 1.3 for additional information.

8.6. Pharmacodynamics

Pharmacodynamics will not be evaluated in this study.

8.7. Genetics

8.7.1. Whole Blood and/or Saliva Samples for Pharmacogenetic Research

Whole blood and/or saliva samples will not be collected for Parts A and B. Only whole blood will be collected for Part C in this study. Genetic research will not be performed.

8.8. Biomarkers

If available, participants' somatic alterations may be obtained at baseline as part of their medical oncology history (see Section 1.3). This study may analyze somatic alterations relevant to study intervention, mechanism of action, the variable response to study drug(s), cell cycle, and pathways associated with cancer.

See Section 9.4.10 for biomarker analyses.

8.8.1. Biomarkers for Part C

This study will analyze biomarkers relevant to study intervention, mechanism of action, the variable response to study drug(s) (including evaluation of AEs or differences in efficacy), cell cycle, immune function, or pathways associated with neuroblastoma. Samples collected will enable examination of these questions through the measurement of biomolecules, including DNA, RNA, proteins, lipids, and other circulating or cellular elements. Derivatives of samples, for example, tumor images, can also be used to identify biomarkers of participant response or resistance. Except for the cases detailed in Section 8.8.1.1 (tumor DNA sequencing without patient-matched germline subtraction) and Section 8.8.1.2 ([circulating tumor DNA] ctDNA sequencing without patient-matched germline subtraction), biomarker analyses will not produce interpretable results on germline DNA and therefore will not lead to the identification of genetic findings. Biomarker analyses using RNA as substrate will avoid the identification of genetic

variants and will focus on quantifying gene expression and reporting tumor somatic gene fusions and other tumor somatic rearrangements. Biomarker analysis results may occur after the clinical study report (CSR) is written and therefore a separate biomarker Data Analysis Plan will be developed.

Samples for biomarker research will be collected as specified in the Schedule of Activities (Section 1.3), where local regulations allow. It is possible that biomarker data for participants in the study have already been generated from samples that were collected and analyzed prior to enrolling in this trial. This may include data generated from genetic analyses. If available, these data may be requested from medical records for use in the research described in Sections 8.8.1.1 and 8.8.1.2, for instance to understand the role of various co-occurring alterations

Samples may be used to develop related research methods or to validate diagnostic tools or assays, but only within the specific research scope described in this protocol. The samples may be analyzed as part of a multi-study assessment of non-genetic factors involved in the response to study intervention or study interventions of this class, and/or to understand study disease or related conditions, within the scope described in this protocol.

All samples will be coded with the participant number. These samples and any data generated can be linked back to the participant only by the study site personnel. Samples will be retained for a maximum of CCI after the last participant visit for the study, or for a shorter period if local regulations and/or ERBs/IRBs impose shorter time limits, at a facility selected by the Sponsor or its designee. This retention period enables use of new technologies, response to questions from regulatory agencies, and investigation of variable response that may not be observed until later in the development of study treatment or after study treatment becomes commercially available. Technologies are expected to improve during the CCI storage period, and therefore, cannot be specifically named. Regardless of the technology utilized, data generated will be used only for the specific biomarker research scope described in this section, and within the limits of this protocol.

8.8.1.1. Tissue Samples for Biomarker Research

Tissue samples for biomarker research will be collected for the purposes described in Section 8.8.1. The following samples for biomarker research will be collected according to the sampling schedule in the Schedule of Activities (Section 1.3), where local regulations allow.

Submission of tumor sample, archival or fresh, obtained prior to initiation of study treatment, will be collected, when available. The most recent sample is desired. Relapse or metastatic sample where available is preferred. The tumor samples will preferably be in the form of a CCI. If this is not possible, approximately ^{cci} slides of freshly prepared unstained 5-micron sections may be provided. Due diligence should be used to make sure that tumor sample, not a normal adjacent or a tumor margin sample, is provided. Samples can be sent at any time during study if not submitted at screening.

Pathology report accompanying tumor tissue will be requested. Pathology reports must be coded with the participant number. Personal identifiers, including the participant's name and initials, must be removed from the institutional pathology report prior to submission. Archival blocks will be sectioned. Sponsor has a right to retain a portion of the submitted tissue, and archival

blocks may be returned to the study site, upon request. Tissue blocks from biopsies collected at baseline or disease progression may be returned to sites if there is available tissue left over, upon request.

Tumor DNA analysis (whole exome or panel DNA sequencing) may be performed with patient-matched germline DNA subtraction. Germline DNA for each patient will originate from DNA extracted from whole blood as described in Section 8.8.1.3. Review of germline DNA sequencing results may be conducted, but only for data quality control purposes. At no point in this process will germline DNA variants be analyzed and interpreted by the research personnel. As such, tumor DNA analysis with germline DNA subtraction will not produce interpretable results on germline DNA, is not considered genetic research, and therefore, will not lead to the identification of genetic incidental findings. Genetic incidental findings are variations present in germline DNA that are discovered unintentionally.

Tumor DNA analysis (whole exome or panel DNA sequencing) may be performed without germline DNA subtraction. When analyzed this way, it may be considered genetic research and the identification of genetic incidental findings is possible. However, the methods used in this study for biomarker analyses are not clinically validated to detect germline variants, and therefore, no clinical conclusions can be derived from them. As such, no genetic findings will be reported to the patients participating in biomarker research, subject to local regulations.

Tumor RNA sequencing analyses quantitate tissue mRNA expression levels, report gene fusions, splice variants, and other somatic rearrangements and do not detect germline variants. Therefore, these analyses are not considered genetic research, and no genetic findings will be identified.

8.8.1.2. Plasma Samples for Biomarker Research

Plasma samples for biomarker research will be collected from participants as specified in the Schedule of Activities (Section 1.3), where local regulations allow.

Plasma samples may also be used for ctDNA analyses. ctDNA analysis may be performed with patient-matched germline DNA subtraction. Germline DNA for each patient will originate from DNA extracted from whole blood as described in Section 8.8.1.3. Review of germline DNA sequencing results may be conducted, but only for data quality control purposes. At no point in this process will germline DNA variants be analyzed and interpreted by the research personnel. As such, ctDNA analysis with germline DNA subtraction will not produce interpretable results on germline DNA, is not considered genetic research, and therefore, will not lead to the identification of genetic incidental findings.

ctDNA analysis may be performed without germline DNA subtraction. In this case, it may be considered genetic research, and the identification of genetic incidental findings is possible. Regardless of whether participant-matched germline DNA subtraction is used or not during the ctDNA analysis, the methods used in this study for biomarker analyses are not clinically validated to detect germline variants, and therefore, no clinical conclusions can be derived from them. As such, no genetics findings will be reported to the patients participating in biomarker research, subject to local regulations.

8.8.1.3. Whole Blood Samples for Biomarker Research

A whole-blood sample for biomarker research will be collected from all participants as specified in the Schedule of Activities (Section 1.3), where local regulations allow. This sample may be used for the extraction of DNA that allows patient-matched germline DNA subtraction during tumor DNA analysis from tissue (Section 8.8.1.1) and ctDNA (Section 8.8.1.2).

8.9. Medical Resource Utilization and Health Economics

Health economics and medical resource utilization parameters will not be evaluated in this study.

8.10. Product Acceptability and Palatability Assessments

The patient and/or caregiver will be asked to provide responses to questions designed to assess the acceptability and palatability of the tablet swallowed whole, dispersed in food or liquid, or dispersed and administered through a nasogastric or gastrostomy tube (Kozarewicz 2014). If the patient is using abemaciclib oral granules, the patient and/or caregiver will be asked to provide responses to questions designed to assess the acceptability and palatability of the oral granules swallowed whole, placed in food or liquid, or dispersed and administered through a nasogastric or gastrostomy tube. The questionnaire for tablet or oral granule acceptability will assess the subject's ability to swallow the drug product as designed. The questionnaire for acceptability and palatability of the tablet or oral granules dispersed in food or liquid will assess the subject's experience relating to the taste, appearance, smell, mouthfeel, and aftertaste of the dispersion and ease of preparing and taking the dispersion. The questionnaire for acceptability of the tablet or oral granules dispersed and administered through a nasogastric or gastrostomy tube will assess the ease of preparation and administration of the dispersion. The appropriate questionnaire will be administered at the time of dosing or within approximately 30 minutes after dosing at Cycle 1 Day 1, Cycle 1 Day 15, and Cycle 2 Day 1. If a patient changes the method of abemaciclib administration or formulation (tablets to granules or vice versa) at any point during the trial, the appropriate questionnaire corresponding to the new administration method or formulation should be completed at the next clinic visit following the method change. The questionnaire will be completed by caregivers (proxy) for patients aged ≤ 5 years. For patients ≥ 6 years old to < 12 years old, both patient and caregiver will complete the questionnaires. For patients ≥ 12 years old, the questionnaire will be self-completed.

9. Statistical Considerations

9.1. Statistical Hypotheses

Parts A and B

Parts A and B of Study JPCS is designed to evaluate

- the PK, safety, and tolerability of abemaciclib in combination with irinotecan and temozolomide (Part A) and abemaciclib in combination with temozolomide (Part B) in pediatric patients with relapsed/refractory solid tumors that have progressed on standard treatment,
- the RP2D, and
- preliminary efficacy.

Lilly hypothesizes that abemaciclib in combination with temozolomide and irinotecan (Part A), abemaciclib in combination with temozolomide (Part B) will be sufficiently tolerable with evidence of clinical activity to support further development.

Part C

Lilly hypothesizes that abemaciclib in combination with dinutuximab, GM-CSF, irinotecan, and temozolomide (Part C) will be sufficiently tolerable and have sufficient anti-tumor activity. The drug combination will be assessed by evaluating the PK, safety, and tolerability of the drug combination in pediatric and young adult patients with relapsed/refractory neuroblastoma.

At the same time, the anti-tumor activity is assessed using Simon's optimal two-stage design (Simon 1989), where the null hypothesis is that the objective response rate (ORR) [REDACTED] CCI and the alternative hypothesis is that the ORR CCI [REDACTED]

9.2. Sample Size Determination

Approximately 30 to 117 patients will be enrolled in this Phase 1b/2 study, with 24 to 60 in Parts A and B and 6 to 57 in Part C. The sample size for Parts A and B is primarily determined by DLTs (up to 6 evaluable patients at a dose level before establishing the MTD), while the sample size for Part C depends on both DLTs and responses. The maximum sample size of 57 in Part C is determined by considering dose finding and ensuring that [REDACTED] CCI patients are treated on the RP2D. The sample size of [REDACTED] CCI is determined using Simon's optimal two-stage design with a power of 80% and a one-sided type I error rate of 0.025, given a null ORR of [REDACTED] CCI against an alternative ORR of [REDACTED] CCI assumed at the RP2D.

9.3. Populations for Analyses

For purposes of analysis, the following populations are defined:

Population	Description
Entered	All participants who sign informed consent/assent (if applicable)
Treated Patients (safety population)	Patients who have been assigned to study treatment and have received at least 1 dose of any study treatment.
Screen Failures	Patients or legal guardian (if applicable) who have signed informed

	consent/assent, do not meet eligibility criteria or due to AEs, physician's decision, etc. and are not enrolled.
--	------------------------------------------------------------------------------------------------------------------

Patients who withdraw from the study before receiving study drug(s) will be replaced and will not be included in the safety or efficacy assessments. Safety analyses will be conducted on all patients who have been exposed to study drug, regardless of whether they are deemed evaluable for other assessments. In Parts A, B, and Stage 1 of Part C, any patient who is discontinued from the study before completing 1 cycle will be deemed DLT non-evaluable for assessment of the combination unless the patient experiences a DLT prior to withdrawal. If a patient is noncompliant during Cycle 1 or receives <75% of doses due to reasons other than drug-related toxicity, he or she will be considered DLT non-evaluable for assessment of the combination and may be replaced. DLT non-evaluable patients may be replaced to ensure that enough patients complete 1 cycle unless accrual to that cohort has stopped due to a DLT.

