4.1.1. Dose Escalation Design for Parts A and B

The dose will be escalated following assessment of toxicity using the standard scoring system, Common Terminology Criteria for Adverse Events (CTCAE) Version 5.0, established by the National Cancer Institute (NCI).

In Part A, patients will begin abemaciclib at Dose Level 1 (70 mg/m^2). After the dose escalation of Part A is completed, one dose level higher than the MTD of abemaciclib in Part A will be used as the starting dose in the dose escalation of Part B, but will not exceed 115 mg/m^2 BID. Three patients are planned for treatment at each dose level; however, the exact number of patients treated at a specific dose level depends on the number of patients within the cohort who experienced a DLT.

Patients will be considered DLT-evaluable if they have either completed the DLT-observation period and received at least 75% of planned doses of each study drug in Cycle 1 or have discontinued study treatment or study participation before completing Cycle 1 due to a DLT or received less than 75% of planned Cycle 1 doses due to drug-related toxicity. Non-evaluable patients may be replaced to ensure that enough patients complete 1 cycle unless accrual to that cohort has stopped due to a DLT.

Following the 3+3 dose escalation scheme, if 0 of 3 patients at a given dose level experience first cycle DLT, the subsequent cohort will enroll at the next higher dose level.

- If 0 of 3 evaluable patients experience a DLT, but safety concerns are present, 3 additional patients may be added to the same dose level cohort to provide additional data following discussion between the investigators and the sponsor.

If 1 of 3 evaluable patients in a cohort experience a DLT, the cohort will be expanded to include 6 patients.

- The dose escalation can proceed if <2 out of 6 evaluable patients experience a DLT.

- If a DLT is observed in ≥ 2 out of a maximum of 6 evaluable patients at any given dose, a safety review will be triggered, dose escalation will cease, and the next lower dose will be considered the MTD.

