4.1.3. Dose-Limiting Toxicity Determination and Maximum Tolerated Dose Definition

A DLT is defined as any of the events according to the NCI CTCAE version 5.0 below if both the following criteria are met:

- The event occurs during the DLT observation period of Cycle 1, between Days 1 and 21, and,
- The event is clinically significant and either definitely, probably, or possibly related to abemaciclib or the combination treatment following discussion between the investigator and Lilly CRP/CRS.

Investigators, together with the Lilly CRP/CRS, can declare a DLT if a patient experiences a significant toxicity deemed to be dose-limiting.

In the event of any Grade 5 AE, enrollment will be suspended, and a thorough safety review will be performed prior to resuming enrollment.

If a patient receives <75% of any planned Cycle 1 study drug doses due to drug-related toxicity, the toxicity will be declared a DLT.

Nonhematological events:

With the exceptions listed below, all Grade ≥ 3 nonhematological AEs will be considered a DLT.

Exceptions:

- Grade 3 diarrhea controlled with supportive care and lasting <72 hours;
- Acute irinotecan-associated diarrhea lasting <7 days and controlled with supportive care;
- Grade ≥ 3 nausea, vomiting, or constipation that is manageable with supportive care and lasts <72 hours;
- Grade 3 mucositis/stomatitis of <72 hours duration;
- Grade 3 fever or infection;
- Grade ≥ 3 electrolyte abnormality that lasts <72 hours, is not clinically complicated, and resolves spontaneously or responds to conventional medical interventions;
- Grade ≥ 3 amylase or lipase that is not associated with symptoms or clinical manifestations of pancreatitis; or
- Aspartate aminotransferase (AST)/ALT elevation resolving to eligibility criteria within 7 days;

Hematological events:

- Cycle Delay: a >14-day delay in the start of a subsequent cycle because of neutropenia or thrombocytopenia in the absence of bone marrow disease progression seen on clinically indicated bone marrow biopsy (if performed).
Note: Patients who experience dose-limiting neutropenia and/or thrombocytopenia will have these events reviewed by the sponsor to discuss attribution (bone marrow disease [baseline and subsequent, if performed and clinically indicated] versus study drugs). Patients with bone marrow disease progression will not be considered to have dose-limiting hematological toxicities.
- Grade ≥ 3 thrombocytopenia with clinically significant bleeding; or

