**Table JPCS.7.1. Analysis Populations**

Population	Description
Entered	All participants who sign informed consent/assent
Treated Patients	Patients who have been assigned to study treatment and have received at least 1 dose of any study treatment.
Screen Failures	Patients or legal guardian (if applicable) who have signed informed consent/assent, do not meet eligibility criteria or due to AEs, physician's decision, etc. and are not enrolled.

Abbreviations: AE = adverse event; DLT = dose-limiting toxicity.

Patients who withdraw from the study before receiving study treatment will be replaced and will not be included in the safety or efficacy assessments. Safety analyses will be conducted on all patients who have been exposed to study treatment, regardless of whether they are deemed evaluable for other assessments. In Parts A, B, and Stage 1 of Part C, any patient who is discontinued from the study before completing 1 cycle will be deemed DLT non-evaluable for assessment of the combination, unless the patient experiences a DLT prior to withdrawal. If a patient is noncompliant during Cycle 1 due to reasons other than drug-related toxicity, he or she will be considered non-evaluable for assessment of the combination and may be replaced. Non-

evaluable patients may be replaced to ensure that enough patients complete 1 cycle, unless accrual to that cohort has stopped due to a DLT.

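### A patient with an observed Cycle 1 DLT who stays on study but misses doses for non-toxicity reasons is classed as non-evaluable and replaceable, so that DLT leaves the 3+3 and Rule A counts

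*Protocol*

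**What the plan says.** Protocol 4.1.1, repeated in SAP 6.1.1, gives three routes to being DLT-evaluable.

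- By completion: the patient finished the observation window and "received at least 75% of planned doses of each study drug in Cycle 1".
- By a DLT that ended treatment: the patient "discontinued study treatment or study participation before completing Cycle 1 due to a DLT".
- By a shortfall that toxicity caused: the patient "received less than 75% of planned Cycle 1 doses due to drug-related toxicity".

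Protocol 4.1.3 adds that a toxicity-caused shortfall is itself a DLT: "If a patient receives <75% of any planned Cycle 1 study drug doses due to drug-related toxicity", that toxicity is declared a DLT.

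Protocol 9.3 approaches the matter from the other side, in two consecutive sentences. The first makes a patient who leaves the study before the end of Cycle 1 non-evaluable, "unless the patient experiences a DLT prior to withdrawal". The second deals with noncompliance in that cycle and with the non-toxicity shortfall. It says of a patient who "receives <75% of doses due to reasons other than drug-related toxicity, he or she will be considered DLT non-evaluable". This second sentence carries no exception for an observed DLT. Replacement is optional, and is ruled out where accrual to the cohort has already stopped for a DLT.

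SAP 7.1.1 has the same two sentences, but the second gives no percentage and refers only to a patient who is "noncompliant during Cycle 1 due to reasons other than drug-related toxicity".

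The 3+3 rules in 4.1.1 and Rule A in 4.1.2 and 9.5 (SAP 6.1.2 and 7.7.2) are stated in terms of evaluable or DLT-evaluable patients.

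**The concern.** A 75% rule exists so that a patient who was barely exposed and had no toxicity does not count as evidence that the dose is safe. That reasoning does not apply to a patient who was under-dosed and had a DLT anyway: the event happened at no more than the planned exposure and is informative about the dose. As written, the rule discards it and lets another patient take the place.

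In cohorts of three to six, one patient decides the outcome. The study is open-label (protocol 6.3), so the reason for missed doses can be recorded with the DLT already known. What is at stake is the count behind dose decisions that have not yet been taken.

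**Working it through.** **1. Patients with a Cycle 1 DLT, read against both protocol sections**

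| The patient | 4.1.1 | 9.3 |
|---|---|---|
| stops because of the DLT | evaluable | evaluable |
| is below 75% because of drug-related toxicity | evaluable | not excluded |
| leaves the study for another reason after the DLT | no route, unless a shortfall was caused by toxicity | evaluable by the first sentence; non-evaluable by the second if also below 75% for a non-toxicity reason |
| stays on study, below 75% for a non-toxicity reason | no route | non-evaluable, replaceable |

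The last row is the gap. The third row is an inconsistency between the two sections and within 9.3.

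**2. Does the toxicity route close the gap?** Only partly. Protocol 6.6.1 suspends treatment for a DLT and allows it to resume, so some shortfalls will be caused by toxicity. But irinotecan and temozolomide are given on Days 1-5, dinutuximab on Days 2-5 and GM-CSF on Days 6-12 (protocol 6.1), while the DLT window runs to Day 21 (4.1.3). A DLT that first appears after those days cannot explain doses of those drugs already missed. No rule says which cause governs a mixed shortfall.

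**3. How many missed doses are enough?** Under the per-drug wording of 4.1.1, the doses needed are 0.75 × planned doses, rounded up.

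- Temozolomide, and irinotecan in Part A: 0.75 × 5 = 3.75, so 4 are needed. Two missed leaves 3/5 = 60%.
- Abemaciclib: 0.75 × 42 = 31.5, so 32 are needed. Eleven missed leaves 31/42 = 73.8%.
- If the same wording applied in Part C: dinutuximab 0.75 × 4 = 3, and two missed leaves 2/4 = 50%; GM-CSF 0.75 × 7 = 5.25, so 6 are needed, and two missed leaves 5/7 = 71.4%.

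Section 4.1.1 is headed Parts A and B, and 9.3 does not say per drug. If 9.3 were read as pooling all Part C doses (42 + 5 + 5 + 4 + 7 = 63), two missed doses would leave 61/63 = 96.8% and exclude nobody. The reading matters and is not stated.

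**4. The plan's own decision rule.** The MTD requires a DLT rate below 33% (protocol 4.1), applied as fewer than 2 of 6. 1/6 = 16.7% proceeds; 2/6 = 33.3% stops. The two statements agree. Remove one DLT patient and replace with one without a DLT, and 2/6 becomes 1/6, or 1/3 becomes 0/3.

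**5. Operating characteristics.** The documents give neither the true DLT rate p nor the share s of patients with a non-toxicity shortfall, so both are assumed: p = 0.33, s = 5%, 10% or 20%.

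The 3+3 chance of clearing a dose at evaluable-patient DLT rate q is (1−q)³ + 3q(1−q)² × (1−q)³. At q = 0.33: 0.301 + 0.444 × 0.301 = 0.434.

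- Current rule, shortfall independent of DLT: q = p, so 0.434 for any s.
- Current rule, shortfall label only on DLT patients: q = p(1−s)/(1−ps).
- DLT patients always evaluable: q = p/(p + (1−p)(1−s)).

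| s | Current, label only on DLT patients: q, chance of clearing | DLT always counted: q, chance of clearing |
|---|---|---|
| 5% | 0.319, 0.456 | 0.341, 0.413 |
| 10% | 0.307, 0.480 | 0.354, 0.390 |
| 20% | 0.283, 0.530 | 0.381, 0.341 |

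Under independence, the chance that six patients include at least one with both a DLT and such a shortfall is 1 − (1−ps)⁶: 9.5%, 18.2% and 33.6% for the three values of s.

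Rule A's threshold and denominator are redacted, so its change cannot be computed.

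**The case against.** The gap is narrow. Patients who stop because of the DLT, who leave after one, or whose shortfall is due to toxicity are mostly protected. Part C Cycle 1 visits are to take place at the site (protocol 1.3.2), so missing two irinotecan or dinutuximab doses for logistic reasons is unlikely; GM-CSF is the drug noted there as possibly outpatient. This stands, and it is why the case is probably infrequent.

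The DLT is not hidden. Safety analyses cover all treated patients, DLTs are listed, the RP2D rests on the totality of the data after discussion between investigators and sponsor, and the MTD definition in 4.1 speaks of patients without the word evaluable. This also stands, but these reviews are discretionary and none restores the DLT to the 3+3 or Rule A count.

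A reader might infer that the rule pushes the selected dose too high in general. The documents do not support that: if the shortfall is unrelated to the DLT, the rate among evaluable patients is still p, and the chance of clearing the dose stays at 0.434. A reader might also infer that every DLT should count whatever dose was taken. That goes too far, because protocol 6.4 lets a patient be considered noncompliant for intentionally or repeatedly taking 125% or more of plan, and a DLT after overdosing is not clean evidence about the assigned dose.

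**Conclusion.** The gap holds on the text of both documents, and it affects the formal counts used for dose decisions. For a single cohort it can reverse the decision, provided the patient is replaced and the replacement has no DLT. On average it is anti-conservative only if the non-toxicity label falls more often on DLT patients, which the open-label setting makes possible but nothing in the documents shows. In the extreme case, at the assumed p = 0.33 and s = 5% to 20%, the chance of clearing the dose rises from 0.434 to between 0.456 and 0.530.

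It should not be read as a finding that Part A's MTD is wrong. That MTD is already set (55 mg/m², protocol 4.1.2; SAP section 4), and the documents report no patient handled this way. The point concerns decisions still to be made.

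**What to change.** In protocol 4.1.1 and 9.3 and SAP 6.1.1 and 7.1.1:

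1. State that any treated patient with a DLT in the observation period is DLT-evaluable and counted as a DLT, even if doses were missed or the patient left for another reason.
2. Apply the exclusion for under-dosing (below 75%, or noncompliance by missed doses) only to patients without a DLT.
3. Review and list separately any DLT that follows dosing above plan.
4. Reconcile the three versions of the threshold (per study drug in 4.1.1, unspecified doses in 9.3, no percentage in SAP 7.1.1) and say which applies in Part C.
5. List all replaced patients with the reason.

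This changes counting, not clinical management. The wording cost is small, but there is a statistical cost: keeping DLT patients while dropping non-DLT patients with a shortfall raises the DLT rate among evaluable patients above p. The last column of the table in the working shows the price in dose clearance, which grows with the shortfall rate. For a dose-finding decision in children that is a defensible direction of error, but it should be stated as a choice.
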